### 354 **Rationale for Study Population**

355 Patients who have a very elevated HbA1c (>10%) are thought to have significant glucose  
356 and lipotoxicity and the current guidelines recommend initiation of a full insulin regimen.  
357 This is a difficult to treat population, as they generally have more advanced disease, less  
358 beta-cell reserve, and, often time, poor compliance. Finding a simpler, safer, and effective  
359 treatment algorithm for these patients would have a great impact on the rate of  
360 comorbidities, as well as healthcare cost. This is also a population traditionally excluded  
361 from all regulatory studies, therefore little information is available on how to best  
362 approach their treatment.  
363

### 364 **Rationale for Study Location**

365 Only patients from the PHHS system will be recruited. PHHS is a county hospital that  
366 provides comprehensive care (primary, specialty, inpatient and outpatient) to the indigent  
367 population of Dallas County. EPIC is the electronic medical record that is deployed at all  
368 sites and covers all aspects of care, including financial data. Therefore PHHS is the ideal  
369 location to conduct this study, as all patient-related information is captured and can be  
370 queried at multiple levels, including cost.  
371

### 372 **Randomization Criteria**

- 373 1. Patient returned a fully completed 7-point glucose profile – suggesting likely  
374 compliance with proposed study procedures.  
375

### 376 **Withdrawal Criteria**

- 377 1. The subject may withdraw consent at any time.  
378 2. Severe drug-related side effects including (but not limited to) acute pancreatitis,  
379 severe nausea and/or vomiting, renal failure, diagnosis of medullary thyroid  
380 cancer, or hypersensitive to any study drug.  
381 3. Pregnancy or intention of becoming pregnant.  
382 4. Subject's diabetes control remains unchanged or becomes worse.

- 383 5. Subject participation in the research is no longer safe  
384 6. The researchers believe that other treatment may be more helpful.  
385 7. The sponsor or the FDA stops the research for the safety of the participants.  
386 8. The sponsor cancels the research.  
387 9. Subject is unable to keep appointments or to follow the researcher's instructions.  
388

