125 pathophysiologic determinants of diabetes: enhance glucose stimulated insulin secretion,  
126 suppress glucagon production, promotes satiety, decreases food intake, improves insulin  
127 sensitivity, lower ectopic fat deposition (i.e. liver steatosis, visceral fat), etc. GLP-1  
128 agonists lower HbA1c by 1.5-2%, have a very low risk of hypoglycemia, and promote  
129 weight loss – all very desirable effects in patients with type 2 diabetes [35]. While this

130 treatment does require an injection, it is very easy to use, does not require continuous  
131 treatment titration, and greatly reduces the need for frequent glucose self-monitoring. All  
132 these attributes make it quite an appealing treatment alternative for patients with type 2  
133 diabetes. In the current diabetes treatment guidelines it is recommended as a second or  
134 third line agent after metformin failure.

135

136 8. The combination of basal insulin and GLP-1 agonists has been proven to be safe and  
137 very effective.

138 A meta-analysis of pooled data from across the LEAD program demonstrated that in  
139 patients with baseline HbA1c of > 9% liraglutide was better than glargine as an add on to  
140 oral hypoglycemic medications with average reduction in HbA1c of 1.9% [39]. Several  
141 other studies support equal or superior HbA1c reduction when a GLP-1 agonist is added  
142 to background therapy and compared to basal insulin, with the additional benefit of  
143 weight loss and minimal hypoglycemia [40-43]. GLP-1 agonist has also demonstrated  
144 superiority when added to maximized basal insulin therapy and metformin, when  
145 compared to prandial insulin alone [40, 44-48]. Furthermore, treatment with GLP-1  
146 agonist in combination with basal insulin was shown to have a synergistic effect on  
147 glycemic control, with GLP-1 agonists exerting an insulin sparing effect, as well as  
148 ameliorating or eliminating the undesirable weight gain associated with insulin therapy.

149

150 The current evidence suggests the combination of metformin, GLP-1 agonist, and basal  
151 insulin to be the most effective and simple strategy to achieve near normal glycemia in  
152 patients with a baseline HbA1c < 10%, while avoiding the side effects of weight gain,  
153 complexity of care, and hypoglycemia associated with insulin alone, or post-prandial  
154 hyperglycemia, weight gain, and hypoglycemia from the association of basal insulin to  

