### 308 **Study Population:**

#### 309 Inclusion Criteria:

- 310 1. Informed consent obtained before any trial-related activities;
- 311 2. Both genders and all ethnicities;
- 312 3. Currently receiving medical care at Parkland Health and Hospital System (PHHS),  
313 Dallas, TX;
- 314 3. Age  $\geq$  18 years;
- 315 4. Diagnosis of Type-2 Diabetes, regardless of time since diagnosis;
- 316 5. Confirmed HbA1c  $>10\%$ .

317

318

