#### 421 *Phone follow-up/ Drug titration visit:*

422 At 2-wk from randomization (visit 3) a phone visit will take place to assess for safety  
423 parameters (particularly hypoglycemia) and perform protocol-driven treatment titration.  
424

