#### 425 *Follow-up visits:*

426 At 1-, 3-, and 6-months (visits 4, 5, 6) patients will be followed-up in person for interim  
427 (and end of study, respectively) evaluations of all outcome parameters, as well as

428 protocol-driven treatment titration. A 7-point glucose profile will be repeated prior to the  
 429 last visit in the study.

430

431 **Interventions:**

432 Both groups will either continue or initiate treatment with metformin. To minimize  
 433 gastrointestinal side effects metformin will be initiated at 500 mg daily (or continued at  
 434 current dose) and titrated weekly in 500 mg increments to the final dose of 1000 mg  
 435 twice daily (or maximum tolerated dose which should be at least 500 mg BID).

436

437 Both groups will be initiated on basal insulin detemir. If new to insulin, this will be  
 438 started at 0.3 units/kg once daily at bedtime and self-titrated based on the study protocol  
 439 (see detemir patient self-titration table). If already on basal insulin, will take the total  
 440 daily dose of basal insulin and perform a 1:1 dose conversion to insulin detemir, which  
 441 will be administered once daily at bedtime, followed by the same titration. Additionally,  
 442 physician-directed titration will occur, if needed, during the scheduled phone and/or  
 443 office visits, as well as any unscheduled patient-initiated visits (phone/in person, if  
 444 applicable). All patients new to insulin will be seen by the diabetes educator to receive  
 445 instruction in insulin injection techniques.

446

447 Detemir patient self-titration table:

Fasting Blood glucose	Change in your insulin dose
<45	Decrease by 5 units
<70 mg/dL	Decrease by 3 units
71- 100 mg/dL	No change in your insulin dose
101-120 mg/dL	Increase by 1 units

448

449 Patients randomized to liraglutide will stop any insulin products besides detemir (if  
 450 applicable), initiate liraglutide at 0.6 mg/day, and dose escalate weekly to 1.2 mg/dl and  
 451 final dose of 1.8 mg/dl. Patients who develop significant and persistent gastrointestinal  
 452 side effects are allowed to down-titrate the dose of liraglutide to 1.2 mg/dl for 1 week  
 453 or until the side effect resolve.

454

455 Patients randomized to meal-time insulin will initiate insulin aspart before each meal.  
 456 Aspart insulin will be initiated at a dose of 0.3 units/kg/day divided among the number of  

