 457 meals taken daily. Meal-time insulin titration, if needed, can be either patient driven (see  
 458 table below) or physician-directed during the scheduled follow-up visits (phone or in  
 459 person), as well as any unscheduled patient-initiated visits (if applicable).

460

461 Novolog patient self-titration table:

Glucose prior to lunch	Change in breakfast insulin dose	Glucose prior to dinner	Change in lunch insulin dose	Glucose prior to bedtime	Change in dinner insulin dose
<54	-2 units	<54	-2 units	<54	-2 units
55-69	-1 unit	55-69	-1 unit	55-69	-1 unit
70-120	No change	70-120	No change	70-130	No change
121-160	+1 unit	121-160	+1 unit	131-180	+1 unit

>160	+2 units	>160	+2 units	>180	+2 units
------	----------	------	----------	------	----------

462

463 **Rescue therapy:**

464 Should any patients randomized to liraglutide treatment experience persistent  
465 hyperglycemia (defined as a confirmed Hb1c>10%) at the 3-mo visit (visit 5), meal-time  
466 insulin aspart will be initiated per the same protocol as above. This is a pre-specified  
467 “treatment failure” end-point. Following initiation of rescue therapy patients will  
468 continue all scheduled visits and procedures through the end of the trial.

469

470 Should any patients randomized to the “standard of care” group experience persistent  
471 hyperglycemia (defined as a confirmed HbA1c >10%) at the 3-mo visit (visit 5),  
472 treatment and insulin titration will continue as scheduled. This is also a pre-specified  
473 “treatment failure” end-point.

474

475 A graphical review of the visit procedures and timing is presented below:

Visit	1	2	3	4	5	6
Time	3-7	0	2 weeks	1	3	6
Type	Office	Office	Phone	Office	Office	Office
Consent	x					
I&E criteria	x					
Randomization criteria		x				
Randomization		x				
Physical exam	x			x	x	x
Height	x					
Vitals (weight, BP, pulse)	x	x		x	x	x
Dietary counseling	x	x	x	x	x	x
Lifestyle counseling	x	x	x	x	x	x
7-point glucose		x				x
Labs (HbA1c, lipids, CMP, Hb)	x				x	x
Dispense trial drug		x		x	x	
Hypoglycemia assessment	X	X	X	x	x	x
Frequency of glucose monitoring				x	x	x
Titrate insulin		x	x	x	x	
Liraglutide titration (if applicable)			x			
Insulin dose assessment		x	x	x	x	x
Compliance assessment				x	x	x
# daily injections				x	x	x
QoL questionnaires (DQOL and SF36)		x				x
AE and SAE assessment		x	x	x	x	x
Pregnancy test (if needed)	x	x		x	x	x
Physician time assessment		x	x	x	x	x

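### Withdrawal criterion 4 lets an unblinded doctor withdraw patients for poor response, overlaps with the rule that retains month-3 treatment failures, and comes with no provision for HbA1c after withdrawal; the expected effect is small and its direction uncertain

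*Combined protocol and SAP*

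**What the plan says.** Item 4 of the Withdrawal Criteria applies when "diabetes control remains unchanged or becomes worse". It has no threshold, time point, confirmation rule or arm. Item 6 is also discretionary: "The researchers believe that other treatment may be more helpful". Items 5 and 9 cover patients for whom participation is no longer safe and those who cannot keep appointments or follow instructions.

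Inclusion criterion 5 ("Confirmed HbA1c" above 10%) sets the entry level. Rescue therapy defines treatment failure as a confirmed HbA1c above 10% at month 3. Liraglutide patients who fail receive aspart and "continue all scheduled visits and procedures through the end of the trial". Control patients who fail carry on with treatment and titration. Safeguards and Precautions repeats these treatment rules.

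The contacts at which a doctor could act are these:
- Week 2: "At 2-wk from randomization (visit 3) a phone visit will take place to assess for safety" and to titrate.
- Later scheduled visits: "At 1-, 3-, and 6-months (visits 4, 5, 6) patients will be followed-up in person for interim" and end-of-study evaluation.
- Unscheduled contacts: titration may occur at "office visits, as well as any unscheduled patient-initiated visits (phone/in person, if" applicable).

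Under Assessments for Efficacy, HbA1c after screening is measured only at months 3 and 6. The Blinding section leaves the treating doctor unblinded. The Statistical Analysis Plan bases the primary comparison on a repeated-measures mixed model in the intention-to-treat (ITT) population. Evaluability of Subjects puts all patients and all collected data into that analysis. Subject Replacement says only that withdrawn patients are not replaced and that 12% drop-out is allowed for.

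**The concern.** Criterion 4 makes poor response itself a ground for removal, and poor response is what the primary endpoint measures. Because entry requires HbA1c above 10%, a patient who is unchanged or worse at month 3, once confirmed, is also a treatment failure. One section lists that patient for withdrawal and another keeps the patient in. The converse does not hold: a fall from 13% to 10.5% is a failure but is not unchanged control. The rules therefore overlap without coinciding.

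The wider gap is what happens next. Including collected data does not say what is collected once a patient leaves, and the sentence that keeps rescued patients on schedule does not cover withdrawn ones. A patient withdrawn at week 2 or month 1 may have no HbA1c after baseline, and one withdrawn between months 3 and 6 may lack the endpoint. If an unblinded doctor removed mainly poor responders on liraglutide, the comparison would tilt towards a false claim of non-inferiority.

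**Working it through.** **The plan's own figure.** Inputs from Sample Size Calculation: margin 0.4, SD 0.5, true difference 0, one-sided alpha 0.025, 44 completers per arm. The non-centrality is 0.4 / (0.5 × √(2/44)) = 0.4 / 0.1066 = 3.75 on 86 degrees of freedom. Power is 0.960, as stated. Enrolment is 88 / 0.88 = 100, also as stated. The sample size is not in dispute.

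**How many patients would show no fall.** The documents give no rate of criterion-4 withdrawals, so a mean fall has to be assumed. The Background says GLP-1 "agonists lower HbA1c by 1.5-2%, have a very low risk of hypoglycemia, and promote" weight loss, so 1.5-2 points is used. That is for the drug class alone; this arm also receives detemir and metformin. The share with no fall is 1 − Φ(fall / SD), and the chance of at least one such patient among 50 is 1 − (1 − p)^50.

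| SD | Fall | Share p | Expected of 50 | Chance of at least one |
|---|---|---|---|---|
| 0.5 | 1.5 | 0.13% | 0.07 | 6.5% |
| 0.7 | 1.5 | 1.6% | 0.80 | 55.5% |
| 0.7 | 2 | 0.21% | 0.11 | 10.1% |

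SD 0.7 is the largest value in the plan's power table. The chance of three or more such patients is below 5% in every row.

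**Applying the rule directly.** Simulation with 50 per arm, a true difference equal to the 0.4 margin, and non-inferiority claimed if the upper 95% limit is below 0.4. Every liraglutide patient with no month-6 fall is removed, and no control patient. Observed month-6 changes are compared by a two-sample test, 100,000 runs.
- SD 0.5: error about 2.6%, hardly different from the nominal 2.5%.
- SD 0.7: error 3.9% (fall 1.5) and 2.7% (fall 2).
- Bias: -0.001 to -0.029 points.
- Rule applied to both arms: error 2.5-3.5%.

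This still assumes perfect foresight of month 6 and no recovery through the mixed model.

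**Bounds for a fixed number lost.** Same setting, with 1 or 3 of 50 lost:

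| Loss | 1 lost | 3 lost |
|---|---|---|
| Liraglutide arm, on recorded month-3 HbA1c, mixed-model type estimate | 2.5% | 2.5-2.6% |
| Liraglutide arm, after month 3 on unrecorded control, month-3 value kept, month 3-6 correlation 0.85 to 0.5 | 3.0-3.9% | 4.2-7.7% |
| Liraglutide arm, before month 3, ranked perfectly on month-6 value | 4.4% | 9.9% |
| As above, selection correlation 0.5 | 3.3% | 5.0% |
| Control arm only, perfect ranking | 1.6% | 0.7% |
| Both arms, perfect ranking | 3.0% | 3.6% |

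In the first row the bias is at most 0.002 SD. In the third it is -0.05 and -0.12 SD, or -0.02 and -0.06 points at SD 0.5 and -0.03 and -0.09 at SD 0.7.

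**The case against.** The strongest reply is that the overlap resolves on ordinary reading. Rescue therapy is specific and the withdrawal list is general; it even includes external stops such as the sponsor cancelling the research. The FDA Approval section records an exception obtained so that liraglutide failures could receive prandial insulin, which would serve no purpose if they were removed. This stands. A reader might infer that the protocol orders month-3 failures out of the trial; the documents do not support that. Withdrawal on the recorded month-3 value is also immaterial, because the model uses that value.

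Second, at week 2 and month 1 the documented response to poor control is titration, and nobody can rank patients on a month-6 value not yet seen. This also stands, and it is why 4.4% and 9.9% are upper bounds for those numbers lost.

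Third, only the liraglutide arm gains a rescue drug. After month 3 a doctor may have more reason to withdraw control patients, which is the conservative direction. That is plausible but not certain.

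Fourth, the statistician's quarterly review with the data safety monitoring board could reveal unequal withdrawal, and treatment failure is a separately compared endpoint. Neither replaces a missing month-6 HbA1c.

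What remains is the missing provision for follow-up. The low count also has limits. It rests on the plan's SDs: at SD 1.0, an assumption outside the plan's table, a fall of 1.5 gives 1 − Φ(1.5) = 6.7%, or 3.3 of 50. It covers criterion 4 only; items 5, 6 and 9 could add losses.

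**Conclusion.** The point holds at low severity. Criterion 4 permits outcome-dependent withdrawal by an unblinded doctor, and the documents neither state which rule prevails nor provide for HbA1c afterwards. The month-3 overlap is a wording matter. The residual risk is judgement-based withdrawal before month 3 or at unscheduled contacts after it.

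At the plan's SDs and an assumed fall of 1.5-2 points, the one-sided error stays between about 2.6% and 3.9% even if all the loss is on the liraglutide side.

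Two stronger conclusions might be inferred, and neither is supported. One is that the false-positive rate is expected to approach 10%: that needs three losses, all on liraglutide, chosen with perfect foresight. The other is that the bias is known to favour liraglutide: nothing in the documents says which arm would lose more poor responders. Nor can a shift comparable to the margin be derived from them. A shift of 0.30 needs a 10-point difference between arms in withdrawals and unseen values 3 points above prediction (0.10 × 3), and the documents support neither input.

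**What to change.** Make three changes of wording in the protocol and analysis plan:

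1. Limit criterion 4 to stopping or changing study drug. This keeps a way to change treatment for patients whose control worsens.
2. State that the Rescue therapy section governs month-3 treatment failures in both arms.
3. State that any patient taken off study treatment, including under items 5, 6 and 9, who has not withdrawn consent still has the scheduled month-3 and month-6 HbA1c, and that these values enter the primary ITT model.

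The cost is two or three sentences and the follow-up of a few off-treatment patients at visits already scheduled. No change to sample size or added assay is needed.

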### 389 **Subject Replacement**

390 Subjects who withdraw or become ineligible will not be replaced. A drop-out rate of 12%  
391 is estimated and already calculated in the recruitment plan.  
392

### 393 **Study Schedule**

#### 394 *Recruitment:*

395 We will recruit patients from the following locations within the PHHS: emergency room  
396 (only if discharged home after the evaluation), primary care clinics, any specialty clinic  
397 (including diabetes clinic). Eligible patients will be informed about the trial by their  
398 treating physician. If agreeable, they will be contacted by the study staff and a screening  
399 appointment scheduled as soon as feasible (within days).  
400

#### 401 *Screening Visit (visit 1):*

402 During the screening visit patients will complete the informed consent process and will  
403 undergo a complete assessment for all inclusion and exclusion criteria. A complete  
404 medical history and comprehensive physical examination will be performed. Blood will  
405 be drawn (if not done within the past 7 days) to assess for all eligibility criteria (HbA1c,  
406 creatinine, liver function tests and pregnancy test, if applicable). Patients will receive an  
407 identification card with information about participation in the study. Patients will be  
408 asked to complete a 7-point glucose profile on the day prior to their next visit.  
409

#### 410 *Randomization (visit 2):*

411 Randomization will occur at the second visit (3-7 days from visit 1-screening). The study  
412 statistician will generate a blocked randomization scheme (1:1) stratified by "any insulin  
413 treatment at time of screening" (yes/no) and BMI (cutoff 37 kg/m^2 – the average BMI of  
414 this study population in our PHHS Diabetes Clinic).  
415

416 At this visit we will obtain a full baseline evaluation of all outcome parameters. All  
417 patients will meet with the dietician to received education regarding recommended  
418 lifestyle modifications. Patient will undergo diabetes education as well as teaching  
419 regarding insulin injection and titration.  
420

#### 421 *Phone follow-up/ Drug titration visit:*

422 At 2-wk from randomization (visit 3) a phone visit will take place to assess for safety  
423 parameters (particularly hypoglycemia) and perform protocol-driven treatment titration.  
424

#### 425 *Follow-up visits:*

426 At 1-, 3-, and 6-months (visits 4, 5, 6) patients will be followed-up in person for interim  
427 (and end of study, respectively) evaluations of all outcome parameters, as well as

428 protocol-driven treatment titration. A 7-point glucose profile will be repeated prior to the  
 429 last visit in the study.

430

431 **Interventions:**

432 Both groups will either continue or initiate treatment with metformin. To minimize  
 433 gastrointestinal side effects metformin will be initiated at 500 mg daily (or continued at  
 434 current dose) and titrated weekly in 500 mg increments to the final dose of 1000 mg  
 435 twice daily (or maximum tolerated dose which should be at least 500 mg BID).

436

437 Both groups will be initiated on basal insulin detemir. If new to insulin, this will be  
 438 started at 0.3 units/kg once daily at bedtime and self-titrated based on the study protocol  
 439 (see detemir patient self-titration table). If already on basal insulin, will take the total  
 440 daily dose of basal insulin and perform a 1:1 dose conversion to insulin detemir, which  
 441 will be administered once daily at bedtime, followed by the same titration. Additionally,  
 442 physician-directed titration will occur, if needed, during the scheduled phone and/or  
 443 office visits, as well as any unscheduled patient-initiated visits (phone/in person, if  
 444 applicable). All patients new to insulin will be seen by the diabetes educator to receive  
 445 instruction in insulin injection techniques.

446

447 Detemir patient self-titration table:

Fasting Blood glucose	Change in your insulin dose
<45	Decrease by 5 units
<70 mg/dL	Decrease by 3 units
71- 100 mg/dL	No change in your insulin dose
101-120 mg/dL	Increase by 1 units

448

449 Patients randomized to liraglutide will stop any insulin products besides detemir (if  
 450 applicable), initiate liraglutide at 0.6 mg/day, and dose escalate weekly to 1.2 mg/dl and  
 451 final dose of 1.8 mg/dl. Patients who develop significant and persistent gastrointestinal  
 452 side effects are allowed to down-titrate the dose of liraglutide to 1.2 mg/dl for 1 week  
 453 or until the side effect resolve.

454

455 Patients randomized to meal-time insulin will initiate insulin aspart before each meal.  
 456 Aspart insulin will be initiated at a dose of 0.3 units/kg/day divided among the number of  
 457 meals taken daily. Meal-time insulin titration, if needed, can be either patient driven (see  
 458 table below) or physician-directed during the scheduled follow-up visits (phone or in  
 459 person), as well as any unscheduled patient-initiated visits (if applicable).

460

461 Novolog patient self-titration table:

Glucose prior to lunch	Change in breakfast insulin dose	Glucose prior to dinner	Change in lunch insulin dose	Glucose prior to bedtime	Change in dinner insulin dose
<54	-2 units	<54	-2 units	<54	-2 units
55-69	-1 unit	55-69	-1 unit	55-69	-1 unit
70-120	No change	70-120	No change	70-130	No change
121-160	+1 unit	121-160	+1 unit	131-180	+1 unit

>160	+2 units	>160	+2 units	>180	+2 units
------	----------	------	----------	------	----------

462

463 **Rescue therapy:**

464 Should any patients randomized to liraglutide treatment experience persistent  
465 hyperglycemia (defined as a confirmed Hb1c>10%) at the 3-mo visit (visit 5), meal-time  
466 insulin aspart will be initiated per the same protocol as above. This is a pre-specified  
467 “treatment failure” end-point. Following initiation of rescue therapy patients will  
468 continue all scheduled visits and procedures through the end of the trial.

469

470 Should any patients randomized to the “standard of care” group experience persistent  
471 hyperglycemia (defined as a confirmed HbA1c >10%) at the 3-mo visit (visit 5),  
472 treatment and insulin titration will continue as scheduled. This is also a pre-specified  
473 “treatment failure” end-point.

474

475 A graphical review of the visit procedures and timing is presented below:

Visit	1	2	3	4	5	6
Time	3-7	0	2 weeks	1	3	6
Type	Office	Office	Phone	Office	Office	Office
Consent	x					
I&E criteria	x					
Randomization criteria		x				
Randomization		x				
Physical exam	x			x	x	x
Height	x					
Vitals (weight, BP, pulse)	x	x		x	x	x
Dietary counseling	x	x	x	x	x	x
Lifestyle counseling	x	x	x	x	x	x
7-point glucose		x				x
Labs (HbA1c, lipids, CMP, Hb)	x				x	x
Dispense trial drug		x		x	x	
Hypoglycemia assessment	X	X	X	x	x	x
Frequency of glucose monitoring				x	x	x
Titrate insulin		x	x	x	x	
Liraglutide titration (if applicable)			x			
Insulin dose assessment		x	x	x	x	x
Compliance assessment				x	x	x
# daily injections				x	x	x
QoL questionnaires (DQOL and SF36)		x				x
AE and SAE assessment		x	x	x	x	x
Pregnancy test (if needed)	x	x		x	x	x
Physician time assessment		x	x	x	x	x
Healthcare cost data extraction						x

476

477 Dietary Modifications:

478 Counseling regarding the type and amount of food consumed with strong encouragement  
479 to count carbohydrates and/or calories will be performed for all patients by the dietitian at  
480 visit 2 and investigator at visits 3-5.

481

482 Lifestyle Modifications:

483 All patients will receive recommendations regarding type/amount/intensity of physical  
484 activity and be provided future goals at visit 1. Reinforcement of these objectives will  
485 take place at visits 2-5.

486

487 **Assessments for Efficacy**

- 488 1. HbA1c – measured at screening, visit 5 (3-months) and end of study (6 months).  
489 Samples are processed immediately and stored at 0-5°C. It will be analysed within 24  
490 hrs at the UT Southwestern Medical Centre Diabetes laboratory using an HPLC  
491 technique. The laboratory is accredited by the National Glycohemoglobin  
492 Standardization Program. HbA1c interassay coefficient of variability is  $\leq 2\%$ , and the  
493 intra-assay variability is  $\leq 0.3\%$ .
- 494 2. Weight - will be measured at each office visit using the same calibrated digital scale,  
495 while patients wearing no shoes and only light clothing.
- 496 3. Total daily insulin dose – will be calculated in units/kg at each visit by summing all  
497 insulin shots of all types over a 24 hrs period. The average of the 3 most recent 24 hrs  
498 prior to each visit will be used.
- 499 4. Number of daily injections – will be counted at each visit, by adding all shots  
500 regardless of the type of insulin. The average of the 3 most recent 24 hrs prior to each  
501 visit will be used.
- 502 5. Systolic and diastolic blood pressure - will be measured in sitting position using an  
503 Omron digital manometer, on the right arm, after 5 minutes of rest.
- 504 6. Lipid profile, liver function test, haemoglobin - will be collected at screening, 3-  
505 months, and end of study in fasting state. The blood will be processed and analysed  
506 immediately by PHS Clinical Laboratory.
- 507 7. 7-point glucose measurement – will be performed by the patient on the day prior to  
508 the randomization visit and prior to the end-of-study visit.
- 509 8. Frequency of glucose monitoring – will be assessed by downloading the glucose  
510 monitor. Average number of readings/day will be recorded at each visit.

511

512 **Assessments for Safety**

513 All safety assessments are performed at each visit, in person or by phone. Any  
514 unanticipated or serious adverse events will be reported to the local IRB and FDA in  
515 accordance with local guidelines.

516

- 517 1. Hypoglycemia – All plasma glucose values  $\leq 70$  mg/dL, as well as values  $>70$   
518 mg/dL when hypoglycemic symptoms have occurred, should be recorded by the  
519 subjects in the blood glucose diaries provided at each visit. The recording should  
520 include:

- 521 • date of hypoglycemic episode

- 522 • time of hypoglycemic episode
- 523 • time of last main meal prior to episode
- 524 • whether the episode was symptomatic
- 525 • whether the episode was in relation to exercise
- 526 • whether seizure or coma developed
- 527 • whether the subject was able to treat him/herself
- 528 • the plasma glucose level before treating the episode

529

530 The following definitions for hypoglycemia will be used:

- 531 • Mild- Symptomatic or asymptomatic hypoglycemia with blood glucose 56-69
- 532 mg/dl and subject was able to treat him/herself
- 533 • Moderate- Symptomatic or asymptomatic hypoglycemia with blood glucose <56
- 534 mg/dl and subject was able to treat him/herself
- 535 • Severe- Blood sugar <70 mg/dl or symptoms highly suggestive of hypoglycemia
- 536 and the subject needed assistance to be treated with carbohydrates, glucagon, or
- 537 other resuscitative actions
- 538 • Nocturnal hypoglycaemia- blood glucose <70 with a time of onset between 00:01
- 539 and 05:59 (both included)
- 540 • Relative Hypoglycemia- Blood glucose >69 mg/dl with symptoms highly
- 541 suggestive of hypoglycemia
- 542 • Probable symptomatic hypoglycemia- Symptoms highly suggestive of
- 543 hypoglycemia but subject did not measure blood glucose.

544

545 2. Other treatment specific side effects

- 546 • Nausea, vomiting, diarrhea, and headache;
- 547 • Abdominal pain suspicious for pancreatitis would prompt immediate physician
- 548 evaluation and laboratory testing for amylase and lipase measurement which
- 549 would be processed immediately and analysed by PHHS Clinical Laboratory.

- 550 3. Pregnancy Test- females of childbearing potential will have urine pregnancy test
- 551 (human chorionic gonadotropin, hCG) performed if clinically indicated in the
- 552 assessment of the investigator. Urine-stick pregnancy test will be performed for
- 553 females of childbearing potential at any time during the trial, if a menstrual period is
- 554 missed or if the participant voices concern.

555

556 **Other Assessments**

557 Treatment satisfaction and quality of life will be assessed at the randomization visit (Visit

558 2) and end of study (Visit 6) using a modified DQoL and SF-36 questionnaires. Total

559 score as well as individual domain scores will be analysed and reported.

560

561 Subject Compliance: Participants will bring all study medication to each appointment for

562 review and study drug will be distributed at each appointment (visit 1, 2, 3, 4, and 5).

563 Percent compliance will be calculated and recorded at each visit.

564

565 Healthcare Cost Assessment: At the conclusion of the study, the EPIC integrated medical  
566 record system will be queried for the data regarding all healthcare related expenditures.  
567 From this information a data subset of diabetes-related expenditure will also be reported.

568

569 Physician Time Assessment: Each physician interaction (office visit or phone visit) will  
570 be timed to compare the two treatment regimens with respect to burden on healthcare  
571 provider's time.

572

573

